Every week between Visits 2 and 3 (weeks 3, 4 and 5), the study personnel contacts a patient by the phone to learn about complaints, AE and need of paracetamol and NSAID intake for the previous 2 weeks. If any AE or need of paracetamol and NSAID intake for over 4 days a week during each of the successive 2 weeks is found, the patient is invited to the clinic for the Unscheduled visit or Premature study discontinuation visit (depending on the visit reason).

Follow-up period (Weeks 3–25)

Visit 3 (Week 6, Day 36 ± 2)

The following procedures will be done:

- Collection of complaints and medical history;
- Recording of concomitant therapy;
- Measurement of body weight;
- Assessment of vital signs (BP, HR, RR, body temperature);
- Physical joint examination;
- Assessment of the patient diary;
- Dispensing of the new patient diary to the patient;
- Completion of algofunctional questionnaire WOMAC with the assessment of pain (WOMAC-A-w₆), stiffness (WOMAC-B-w₆), functionality (WOMAC-C-w₆) subscales and total score (WOMAC-T-w₆) ("Week 6" values);
- Patient's assessment of the treatment efficacy, OEP-w₆ value (per the scale from 1 – evident aggravation to 6 – significant improvement);
- Investigator's assessment of the treatment efficacy, OEI-w₆ value (per the scale from 1 – evident aggravation to 6 – significant improvement);
- Assessment of the total number of paracetamol tablets taken per the patient diary (one tablet = 500 mg), value PARACETAMOLw6;
- Assessment of the total number of NSAID tablets taken, value NSAID-w₆
- Complete blood count;

- Blood biochemistry: glucose, ALT, AST, ALP, GGTP, total bilirubin, creatinine, uric acid;
- Coagulogram (APTT, PT, prothrombin index, fibrinogen);
- Urine analysis;
- Express urine pregnancy test for women with the preserved reproductive potential;
- AE assessment;
- Assessment of the subject exclusion criteria.

On Weeks 8, 10 and 12, the study personnel contacts the patient by the phone to learn about complaints, adverse events (AE) and need of paracetamol and NSAID intake for the previous 2 weeks. If any AE or need of paracetamol intake for over 4 days a week during each of the successive 2 weeks is revealed, the patient is invited to the clinic for the unscheduled visit or premature study discontinuation visit (depending on the visit reason).

Visit 4 (Week 13, Day 84 ± 2)

The following procedures will be done:

- Collection of complaints and medical history;
- Recording of concomitant therapy;

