- Measurement of body weight;
- Assessment of vital signs (BP, HR, RR, body temperature);
- Physical joint examination;
- Assessment of the patient diary;
- Dispensing of the new patient diary to the patient;
- Completion of algofunctional questionnaire WOMAC with the assessment of pain (WOMAC-A-w₁₃), stiffness (WOMAC-B-w₁₃), functionality (WOMAC-C-w₁₃) subscales and total score (WOMAC-T-w₁₃) ("Week 13" values);
- Patient's assessment of the treatment efficacy, OEP-w₆ value (per the scale from 1 – evident aggravation to 6 – significant improvement);
- Investigator's assessment of the treatment efficacy, OEI-w₁₃ value (per the scale from 1 evident aggravation to 6 significant improvement);

- Assessment of the total number of paracetamol tablets taken per the patient diary (one tablet = 500 mg) beginning from day 1, value PARACETAMOL-w₁₃;
- Assessment of the total number of NSAID tablets taken, value NSAID-w₁₃
- Complete blood count;
- Blood biochemistry: glucose, ALT, AST, ALP, GGTP, total bilirubin, creatinine, uric acid;
- Coagulogram (APTT, PT, prothrombin index, fibrinogen);
- Urine analysis;
- Express urine pregnancy test for women with the preserved reproductive potential;
- AE assessment;
- Assessment of the subject exclusion criteria.

On Weeks 15, 17, 19, 21 and 23, the study personnel contacts the patient by the phone to learn about complaints, adverse events (AE) and need of paracetamol and NSAID intake for the previous 2 weeks. If any AE or need of paracetamol or NSAID intake for over 4 days a week during each of the successive 2 weeks is revealed, the patient is invited to the clinic for an unscheduled visit or premature study discontinuation visit (depending on the visit reason).

Visit 5 (Week 25, Day 169 ± 2)

The following procedures will be made:

- Collection of complaints and medical history;
- Recording of concomitant therapy;
- Measurement of body weight;
- Assessment of vital signs (BP, HR, RR, body temperature);
- Physical joint examination;
- Assessment of the patient diary;
- Completion of algofunctional questionnaire WOMAC with the assessment of pain (WOMAC-A-w₂₅), stiffness (WOMAC-B-w₂₅), functionality (WOMAC-C-w₂₅) subscales and total score (WOMAC-T-w₂₅) ("Week 25" values);

- Patient's assessment of the treatment efficacy, OEP-w₂₅ value (per the scale from 1 – evident aggravation to 6 – significant improvement);

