- Investigator's assessment of the treatment efficacy, OEI-w₂₅ value (per the scale from 1 evident aggravation to 6 significant improvement);
- Assessment of the total number of paracetamol tablets taken per the patient diary (one tablet = 500 mg) starting from day 1, value PARACETAMOL-w₂₅;
- Assessment of the total number of NSAID tablets taken per the patient diary starting from day 1, value NSAID-w₂₅,
- Complete blood count;
- Blood biochemistry: glucose, ALT, AST, ALP, GGTP, total bilirubin, creatinine, uric acid;
- Coagulogram (APTT, PT, prothrombin index, fibrinogen);
- Urine analysis;
- Express urine pregnancy test for women with the preserved reproductive potential;
- AE assessment.
- In case of planned completion of the study and completion of all procedures provided in the clinical study protocol, the patient will be provided with studied medical device NOLTREX regardless of the treatment group to which the patient was assigned. In this case the patient will receive 4 packages of NOLTREX which corresponds to one treatment course.

Unscheduled visit

Unscheduled visits will be made as necessary, for example, in the event of aggravation of the studied medical condition, AE or intolerability of the study MD or placebo therapy. When an unscheduled visit is made, regardless of its reason, the investigator makes the following procedures and completes corresponding eCRF pages (Unscheduled visit):

- Collection of complaints and medical history;
- Recording of concomitant therapy;
- Measurement of body weight;
- Assessment of vital signs (BP, HR, RR, body temperature);

- Physical joint examination;
- Assessment of the patient diary;
- AE assessment.

If clinically indicated and meeting the criteria, any of the study procedures can be additionally made on the unscheduled visit by the decision of the Principal Investigator.

Premature study discontinuation visit

• On the premature study discontinuation visit, the same procedures are made as on Visit 5

Main parameters of efficacy and safety assessment

rs of Primary endpoint – change of the total WOMAC score (WOMAC-T) safety on Visit 5 (Week 25) in comparison with baseline on visit 1 (Week 1).

Secondary endpoints:

- Change of the total WOMAC score (WOMAC-T) on Visit 4 (Week 13) in comparison with baseline on Visit 1 (Week 1);
- Change of the pain subscale score (WOMAC-A) on Visit 3 (Week
 6), Visit 4 (Week 13) and Visit 5 (Week 25) and in comparison with baseline on Visit 1 (Week 1);

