- 3) Varus or valgus deformation of the target knee joint;
- 4) Instability of the target knee joint;
- 5) Active inflammation of the target knee joint (edema, hyperemia, present effusion) at the study entry;
- 6) Microcrystalline arthropathies;
- 7) Systemic inflammatory disease (rheumatoid arthritis, systemic lupus erythematosus, etc.);
- 8) Seronegative spondiloarthritis and reactive arthritis;
- Inflammatory diseases of the skin and soft tissues in the proposed injection site for the study MD or placebo in the target joint;
- 10) History of venous thrombosis and thromboembolias;
- 11) Coagulogram abnormalities (APTT, prothrombin time, prothrombin index, fibrinogen);
- 12) Inflammatory changes in the complete blood count (leukocytosis, increase of erythrocyte sedimentation rate [ESR]);
- 13) Platelet count abnormality (in accordance with the reference ranges of the local laboratory;
- 14) Increase of rheumatoid factor level;
- 15) Increase of uric acid level > 360 μmol/l;
- 16) Diabetes mellitus:
- 17) Hemophilia and other hemorrhagic diatheses, as well administration of anticoagulants and disaggregants;
- 18) Positive results of HIV, HBs-Ag, anti-HCV, RW tests;
- 19) Intra-articular injection to the target knee joint:
 - MD NOLTREXTM within 24 months prior patient's inclusion to the study;
 - hyaluronates within 6 months prior patient's inclusion to the study;
 - glucocorticosteroids within 1 month prior the study inclusion;
 - non-steroidal anti-inflammatory drugs (NSAID) within 3 weeks prior patient's inclusion to the study.

- 20) Oral administration of non-steroidal anti-inflammatory drugs (NSAID) within 2 weeks prior the study inclusion;
- 21) Necessity of systemic glucocorticosteroids intake in any dosage form;
- 22) Paracetamol administration within 48 hours prior the study inclusion;
- 23) Pregnancy and lactation;
- 24) Hypersensitivity to components of the study MD or placebo;
- 25) Severe liver disorder determined as the increase of one of the values: ALT, AST, ALP, total bilirubin, GGTP more than 3 times the upper limit of normal;
- 26) Renal diseases with the glomerular filtration rate estimated per Cockraft-Gault formula less than 60 ml/min/1.73 m² (III-V stage chronic renal disease [CRD]);
- 27) Clinically manifested hip osteoarthritis;
- 28) History of knee and coxofemoral endoprosthesis;
- 29) Acute infectious diseases or infectious aggravations of chronic diseases (respiratory infections) within one month prior the study inclusion;

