- 30) Severe decompensated chronic or acute diseases and other conditions which, by the opinion of the study physician, may preclude the patient's participation in the study or affect the study results.

Subject exclusion criteria

- Ethics Committee, regulatory bodies or the Sponsor terminate the study or participation of the clinical site in the study for any reasons;
 - Need in paracetamol or NSAID intake due to knee osteoarthritis 4 days a week or more during 2 successive weeks;
 - 3) The investigator makes the decision that a patient should discontinue the study in the best interests of the patient;
 - Informed consent revocation (patient's unwillingness to continue the study);
 - 5) Major deviation from the study protocol;
 - Individual intolerability or contraindications to the study MD, placebo or paracetamol;
 - AE/SAE which requires examination and/or treatment affecting significantly the study procedures (in particular, development of active arthritis or hemarthrosis of the target knee joint);

- 8) Erroneous study inclusion (for example, the patient was included with a violation of the protocol inclusion/non-inclusion criteria);
- 9) A patient has non-inclusion criteria during the study;
- 10) A patient takes/needs additional treatment which can affect the study result or patient's safety (see section "Disallowed concomitant therapy");
- 11) Other conditions or events which require, by the opinion of the study physician, the patient's exclusion from the study.
- 12) Injury of the studied joint.

Disallowed concomitant therapy

- 1. Glucocorticosteroids in any dosage form;
- 2. Any intra-articular or peri-articular injections, physical therapy, as well other therapeutic or rehabilitation measures for knee osteoarthritis, except the study procedures;
- NSAIDs and analgesics including the local ones (except for paracetamol and NSAIDs permitted by the protocol in cases when paracetamol is ineffective);
- 4. Paracetamol intake in dose over 4000 mg a day;
- 5. the use of one of the NSAIDs permitted by the Protocol in doses exceeding those permitted by the Protocol (permitted drugs and doses: diclofenac potassium 50 mg 2 times a day, diclofenac sodium tablets 75 mg 2 times a day, naproxen tablets 500 mg 2 times a day, naproxen sodium tablets 550 mg 2 times a day, meloxicam tablets 7.5 mg once a day, celecoxib tablets 200 mg 2 times a day);
- use of NSAID in combination with paracetamol or combination of two or more NSAID;

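### Exclusion criterion 9, as worded, ends follow-up for a laboratory deviation first found after the last injection, so the Week 25 WOMAC-T is never collected and is filled by LOCF

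*Protocol*

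**What the plan says.** The protocol synopsis, Subject exclusion criteria, item 9, reads in full: "A patient has non-inclusion criteria during the study". Four of the non-inclusion criteria it points to are laboratory findings with no time anchor:

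- Criterion 11: "Coagulogram abnormalities (APTT, prothrombin time, prothrombin index, fibrinogen".
- Criterion 12: "Inflammatory changes in the complete blood count (leukocytosis, increase of erythrocyte sedimentation rate [ESR".
- Criterion 13: "Platelet count abnormality (in accordance with the reference ranges of the local laboratory".
- Criterion 15: "Increase of uric acid level", with a limit of 360 μmol/l.

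Under Patient visits, injections are given at Visit 1 (Day 1) and, if the investigator so decides, at Visit 2 (Day 8). No blood panel is listed at either visit. Blood count, biochemistry including uric acid, and coagulogram ("Coagulogram (APTT, PT, prothrombin index, fibrinogen") are repeated at Visits 3, 4 and 5. Visits 3 and 4 also list "Assessment of the subject exclusion criteria"; Visit 5 does not.

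An excluded patient has a premature discontinuation visit with the Visit 5 procedures, and no later follow-up is described. SAP 2.8.1 keeps the patient in the ITT set, and SAP 2.6 fills a missing primary endpoint by LOCF. SAP 2.6 provides no imputation for other parameters.

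A patient who completes as planned receives a further course: "the patient will be provided with studied medical device NOLTREX regardless of the treatment group to which the patient was assigned".

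**The concern.** A rule that stops injections when a contraindication appears has an obvious purpose. Here the scheduled bloods that could trigger it come only after the injections are over. The rule then removes the patient from follow-up, and with that the primary endpoint, although the Week 13 and Week 25 visits are already in the schedule.

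Two things are at stake. First, the plan assumes a slow onset (Study methodology) and chose Week 25 because the earlier study showed the greatest effect at 6 months (Justification of the sample size). A WOMAC-T carried forward from about Week 6 or Week 13 would therefore tend to understate the Week 25 difference. Second, scheduled laboratory follow-up stops after the discontinuation visit for the patients whose values deviated, and the by-visit safety summary in SAP 2.1.4 loses their later results.

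**Working it through.** **1. Does the wording reach laboratory deviations during follow-up?** Exclusion criteria 3 and 11 contain an investigator-judgement clause; criterion 9 does not. Criterion 8 already covers erroneous inclusion, so criterion 9 adds something only for conditions that arise later. Non-inclusion criteria 5, 19, 20, 22 and 29 are tied to study entry or to a period before it; 11, 12, 13 and 15 are not. On the supplied text the answer is yes.

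**2. Timing** (from Patient visits).

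- Last possible injection to first scheduled post-baseline panel: 36 − 8 = 28 days. Trial injections avoided by exclusion on a scheduled result: 0.
- Age of a value carried from Visit 3 to Day 169: 169 − 36 = 133 days (19 weeks). From Visit 4: 169 − 84 = 85 days.
- A deviation first found at Visit 5 does no harm, because WOMAC is completed at that visit and exclusion is not reassessed.

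**3. The plan's own power figure.** ANCOVA F test with λ = f²N, numerator df 1, denominator df = N − 2 groups − 2 covariates, α = 0.05. With f = 0.25 and N = 128: λ = 0.0625 × 128 = 8.0, df = 124, critical F = 3.91755, power = 0.80136. These are the printed values, and the plan rounds 128 up to 130. For all 144 randomized patients: λ = 9.0, df = 140, power = 0.846.

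**4. Allowance for all exclusions.** 144 − 130 = 14 patients, or 14/144 = 9.7%. If the flag rate per patient per visit is q and Visits 3 and 4 are independent, 1 − (1 − q)² = 0.0972 gives q = 5.0%. If the same patients are flagged twice, q = 9.7%.

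**5. Illustration under assumed flag rates.** The documents give none. The eight tests are APTT, PT, prothrombin index, fibrinogen, leukocytes, ESR, platelets and uric acid. The simulation uses latent normal values at screening, Visit 3 and Visit 4, with 1.5 million patients per case, keeping only patients with no flag at screening. Assumed correlations are 0.2 between tests at a visit, 0.5 between repeats of a test, and 0.1 to 0.2 for a different test at a different visit.

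For power, N = 144 and the effect becomes f = 0.25 × [1 − m(1 − r)]. Here m is the fraction excluded and r the assumed share of the Week 25 effect present in the carried value. All other patients are taken as observed.

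| Flag rate per test | Excluded at Visit 3 or 4 | Patients of 144 | Power, r = 0.5 | Power, r = 0.25 to 0.75 |
|---|---|---|---|---|
| none | 0 | 0 | 0.85 | 0.85 |
| 0.5% | 5.8–6.2% | 8–9 | 0.82–0.83 | 0.81–0.84 |
| 1% | 10.2–11.2% | 15–16 | 0.80–0.81 | 0.78–0.83 |
| 2% | 17.4–19.4% | 25–28 | 0.77–0.78 | 0.72–0.81 |

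Example: m = 0.102, r = 0.5 gives f = 0.25 × (1 − 0.051) = 0.2372 and power 0.807. With seven tests the exclusions are 5.2–5.5%, 9.3–10.0% and 15.9–17.5%. The 2% row is an upper reference, since it would flag 12 to 13.5% of unselected patients at a single visit.

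Power reaches 0.80 at m = 8.0% (11.5 patients) for r = 0.25, 11.9% (17.2) for r = 0.5 and 23.9% (34.4) for r = 0.75. At a 1% flag rate about 55% of these exclusions fall at Visit 3. If those carry r = 0.5 and the Visit 4 exclusions carry r = 0.75, power is 0.81–0.82 at 1% and 0.79 at 2%.

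**The case against.** **The operative rule may lie elsewhere.** SAP 2.5 places the participant termination rules in section 6.3, which is not supplied. That section may require confirmation or clinical significance, and SAP 2.1.4 speaks of clinically significant laboratory changes. This stands. A reader might infer that one unconfirmed out-of-range value must exclude a patient in practice; that is only the literal reading of the supplied text. The wording in SAP 2.1.4, for its part, governs safety tabulation, not exclusion.

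**Avoided injections are not the only safety purpose.** The gel resorbs slowly, and paracetamol or NSAIDs may be used during follow-up, so a new coagulation or platelet deviation can still matter after Day 8. This stands and shapes the fix. It is a reason to manage treatment, not to stop measuring outcome. A reader might also infer that criterion 9 has no safety role because the safety-exclusion endpoint counts only criteria 2, 3, 6 and 7. That list also omits criterion 10, whose text mentions patient safety, so the inference fails.

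**No recorded data are discarded.** A reader might think that an observed Week 25 score is overwritten. It is not: the score is never collected. The discontinuation visit supplies a WOMAC and a laboratory panel, and if results come back late that WOMAC may be later than Visit 3 or 4. The ages in step 2 are therefore approximate.

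**Harm is not demonstrated.** The flag rates, correlations and carried share are all assumed, and at 0.5 to 1% per test with half the effect carried, power stays at 0.80 or above. This stands.

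**The remedy is partial.** Other exclusions that end follow-up, such as criteria 2 and 10, are untouched. That is true, but it is no reason to keep an avoidable loss here.

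**Conclusion.** The point holds for the supplied text. Criterion 9 ends follow-up on a scheduled laboratory result that comes too late to spare any trial injection, and it leaves the primary endpoint to LOCF when it could have been observed. Amending it is worthwhile; the trial does not fail without the change.

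The size is unknown because the documents give no deviation rate. The table in the working shows only what assumed rates would do, taking the plan's f = 0.25 at face value and counting no other exclusions. A reader might conclude that the 10% exclusion rate or the 80% power is breached; the documents do not support that. Nor do they suggest bias in favour of the device: chance laboratory flags should be unrelated to arm, so the expected direction is dilution. Confidence is medium, chiefly because section 6.3 cannot be read.

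**What to change.** Amend exclusion criterion 9 as follows:

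- A non-inclusion criterion met before the last injection stops further injections.
- A laboratory deviation under criteria 11, 12, 13 or 15 first found after the last injection does not by itself end follow-up. The patient completes the remaining scheduled visits and enters the ITT analysis with the observed Week 25 WOMAC-T.
- Withdrawal for safety stays available under exclusion criteria 3, 7 and 11.
- Rescue NSAIDs are restricted where a coagulation or platelet deviation requires it.
- The end-of-study NOLTREX course is withheld while a contraindicating deviation persists. This is needed because a patient kept to planned completion would otherwise become entitled to it.

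If section 6.3 already works this way, the amendment only brings the synopsis into line.

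The cost is a short protocol amendment with no new visits. The downside is that some Week 25 values will be observed under restricted rescue use or added treatment; these should be flagged in the data.

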- 7. Rehabilitation measures due to knee osteoarthritis;
- 8. Physical therapy in knee osteoarthritis;
- 9. Acupuncture;
- 10. Surgeries and arthroscopies of the target knee joint.
- 48 hours prior the visits where the assessment of pain intensity in the knee joint (Screening visit, Visits 1-7) is made paracetamol or NSAID intake is not allowed.

Justification of the sample size

The calculation of the sample size is based on the study results of product Noltex in knee osteoarthritis (osteoarthrosis) (N.V. Zagorodniy et al. Administration of new biopolymer material "Noltrex" in complex treatment of patients with knee osteoarthritis. 2012, v. 17, №6, p. 49-52)

[3]. The use of NSAID Movalis in the study during the first 10 days does not interfere with assessment of results in 13 and 25 weeks.

As the study primary endpoint, we selected the change of the total WOMAC score of the affected joint (WOMAC total), at Visit 7(Week 25) in comparison with baseline at Visit 1 (Week 1). The selection of assessment point "Week 25" is related to the fact that Noltrex effect was the greatest in the abovementioned study in 6 months after the administration, subsequently the product effect was reduced. The additional endpoint – change of total WOMAC score (WOMAC total) on Visit 6 (Week 13) in comparison with baseline on Visit 1 (Week 1) will be used for assessment of the onset of the MD effect in 3 months after the administration.

The following assumptions were used for calculations:

- 1) Two groups (fixed factor A) Noltrex and placebo
- The initial value of the WOMAC score and the total dose of NSAIDs obtained during the study as covariates
- 3) Effect size 0.25: calculated based on the data from the publication presented above in which the value of intergroup differences with regards to variability was up to 100 scores, and variability (standard deviation) up to 400 scores
- 4) Significance level = 5% (type I error α = 0.05)
- 5) Power 80% (II type error β = 0.20)
- Statistical model analysis of covariance (baseline-adjusted) with fixed factors of group
- 7) Study exclusion rate will not exceed 10%
- 8) Non-inclusion rate in selection (screening) period will not exceed 15%

The sample size (number of completed cases) was calculated using applied software package G*Power 3.1.9.2 with the abovementioned assumptions:

= 3.9175498

F tests - ANCOVA: Fixed effects, main effects and interactions

Analysis:	A priori: Compute required sample size		
Input:	Effect size f	=	0.25

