## 2 Description of statistical methods

### 2.1 Description of statistical methods to be used

Statistical analysis will be carried out using specialized software, the selection of which will be carried out during the preparation of the statistical analysis plan.

Continuous (quantitative) data will be presented using the number of observations, arithmetic mean, 95% confidence interval (CI) for mean, standard (mean-square) deviation, median, interquartile range (25th and 75th centile), minimum and maximum.

Qualitative data (ordinal, nominal) will be presented using absolute frequencies (number of observations), relative frequencies (percent) and 95% CI.

Unless otherwise specified in the statistical analysis plan, statistical tests will be two-sided with a 5% confidence level.

The medical history and AEs will be encoded using the MedDRA classifier in the current version. Concomitant and prior therapy will be encoded using the ATX classifier.

This section briefly describes the planned analysis. The full analysis will be described in the statistical analysis plan.

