# 2.3 Planned number of participants in a clinical trial with justification of sample size

The calculation of the sample size is based on the study results of the medical device NOLTREX TM for OA (osteoarthritis) of the knee joint (N. V. Zagorodny et al. The use of new biopolymer material Noltrex in the complex treatment of patients with gonarthrosis. 2012, t. 17, No. 6, p. 49-52)[3]. Application in this study during the first 10 days of NSAID Movalis does not affect the assessment of results after 13 and 25 weeks.

As the primary endpoint in the study the change in total score on the WOMAC scale in the affected joint (WOMAC total) was chosen, at Visit 7 (week 25) compared to the basal value at Visit 1 (week 1). The choice of "Week 25" assessment point is related to the fact that in the above study the effect of medical device NOLTREX TM was maximal after 6 months from the injection, and then the effect of the treatment was decreasing. An additional endpoint - a change in the total score on the WOMAC

scale (WOMAC total) at Visit 6 (week 13) compared to the basal value at Visit 1 (week 1) will be used to assess the onset of the effect of medical device after 3 months from the injection.

For the calculations the following assumptions were used:

- 1) Two groups (fixed factor A) medical device NOLTREXTM and placebo
- 2) Baseline of WOMAC level and the total dose of NSAIDs received in the duration of study as covariates
- 3) Effect size 0.25: calculated on the basis of data from the above publication, in which the magnitude of differences between groups, taking into account the variability, was up to 100 points, and the variability (standard deviation) up to 400 points
- 4) Level of significance = 5% (type I error  $\alpha$  = 0.05)
- 5) Power 80% (type II error  $\beta$  = 0.20)
- 6) Statistical model covariance analysis (adjusted for the initial value) with fixed factors of the group
- 7) Drop-outs during the study will not exceed 10%.
- 8) Drop-out during inclusion period (screening) will not exceed 15%.

Calculations of the sample size (the number of completed cases) were performed using the G\*Power 3.1.9.2 software package with the above assumptions:

F tests - ANCOVA: Fixed effects, main effects and interactions

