A priori: Compute required sample size Analysis: Input: Effect size f = 0.25= 0.05α err prob Power (1–β err prob) = 0.80= 1 Numerator df Number of groups = 2 Number of covariates = 2 = 8.0000000 Output: Noncentrality parameter  $\lambda$ Critical F = 3.9175498Denominator df = 124 = 130 Total sample size Actual power = 0.8013621

In this case, taking into account rounding, the study should complete 130 patients (65 in each group), for which it is necessary to randomize 144 patients (72 in each group).

Accordingly, to achieve the required number of randomized patients, it is necessary to screen up to 170 patients.

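### The sample size enters a standardised difference d = 100/400 = 0.25 as Cohen's f, which for two groups is d/2 = 0.125; on the stated inputs, power is about 29%, not 80%.

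*Protocol*

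**What the plan says.** The sample-size justification appears in the protocol synopsis (Justification of the sample size) and again in SAP 2.3. Assumption 3 in the protocol reads "Effect size 0.25: calculated based on the data from the publication presented above", and adds that the intergroup difference "was up to 100 scores, and variability (standard deviation) up to 400 scores". SAP 2.3 words it almost identically: "Effect size 0.25: calculated on the basis of data from the above publication", with a difference between groups that "was up to 100 points, and the variability (standard deviation) up to 400 points".

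The G*Power block (F tests, ANCOVA: fixed effects, main effects and interactions) then takes "Effect size f = 0.25" with alpha 0.05, power 0.80, numerator df 1, two groups and two covariates. It reports noncentrality 8.0, critical F 3.9175498, denominator df 124, total sample size 130 and "Actual power = 0.8013621". From this come 130 completers (65 per group), 144 randomised (72 per group) and up to 170 screened.

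Neither document mentions a conversion from d to f, a residual SD, or a correlation between the covariates and the outcome.

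**The concern.** A difference between two means divided by a standard deviation is Cohen's d. G*Power's ANCOVA routine asks for Cohen's f, the standard deviation of the group means divided by the within-group standard deviation. With two equal groups each mean lies half the difference from the grand mean, so f is half of d. Entering d where f is asked for doubles the assumed effect and cuts the required sample size by a factor of about four.

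This is the only power statement for the primary endpoint, and it stands in both documents. If it is wrong, a non-significant result may be read as evidence from a trial with 80% power to detect a 100-point benefit when the design has nothing like that power. The error does not affect the type I error, the treatment estimate or its confidence interval; it affects what the trial can be expected to detect and how a null result should be read.

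**Working it through.** **Inputs** (protocol, Justification of the sample size; SAP 2.3): difference 100, SD 400, alpha 0.05, 2 groups, 2 covariates, 130 completers, 144 randomised. SAP 2.1 says "statistical tests will be two-sided with a 5% confidence level"; an F test with numerator df 1 is the matching two-sided test.

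**Method.** Noncentral F with lambda = f² × N, df1 = 1, df2 = N − groups − covariates = N − 4; power is the probability that this F exceeds the 5% critical value.

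**Step 1: reproduce the plan's figure.** With f = 0.25 the smallest N reaching 80% is 128:

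- lambda = 0.0625 × 128 = 8.0
- df2 = 128 − 4 = 124
- critical F = 3.91755
- power = 0.80136

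These agree with the printed output, so f = 0.25 is what was run. At N = 130 with the same f, lambda is 8.125, df2 is 126 and power is 0.8075. The printed lambda, df and power therefore belong to N = 128, not to the 130 printed beside them. SAP 2.3 refers to rounding, and the effect is trivial.

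**Step 2: convert the effect size.** d = 100/400 = 0.25. For two equal groups f = (100/2)/400 = 0.125. Conversely, f = 0.25 means d = 0.50, which is 200 points at SD 400 or 100 points at a residual SD of 200.

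**Step 3: power on the stated inputs, f = 0.125.**

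| N analysed | lambda | df2 | Power |
|---|---|---|---|
| 128 | 2.000 | 124 | 28.9% |
| 130 | 2.031 | 126 | 29.3% |
| 144 | 2.250 | 140 | 31.9% |

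A normal approximation with 65 per arm gives 29.6%. The smallest N for 80% power is 505, or 506 with equal arms. At N = 130, 80% power is reached at f = 0.2476, a difference of 2 × 0.2476 × 400 = 198 points.

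**Step 4: allow for covariate adjustment.** The f in this routine refers to the SD left after adjustment. If 400 is unadjusted and the multiple correlation of the covariates with the outcome is r, the residual SD is 400 × √(1 − r²) and f = 0.125/√(1 − r²). The documents give no r, so the values below are assumptions.

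| r | Residual SD | f | Power, N = 130 | Power, N = 144 |
|---|---|---|---|---|
| 0 | 400 | 0.125 | 29% | 32% |
| 0.5 | 346 | 0.144 | 37% | 41% |
| 0.7 | 286 | 0.175 | 51% | 55% |
| 0.8 | 240 | 0.208 | 65% | 70% |
| 0.866 | 200 | 0.250 | 81% | 85% |

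Reaching f = 0.25 means halving the SD: √(1 − r²) = 0.5, so r = √0.75 = 0.866.

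**The case against.** The strongest reply is that 29% is a floor rather than a settled figure. The planned analysis adjusts for baseline WOMAC, and if the published 400 is a raw SD, adjustment raises power. The main analysis is also on the ITT set with LOCF for the primary endpoint (SAP 2.1.2, 2.6 and 2.8.1), so the number analysed should be nearer 144 than 130. With r = 0.7 and 144 patients, power is 55%. This stands as a qualification: it would be too strong to say without condition that the trial is more likely to miss a 100-point effect than to find it. It does not restore the 80% claim. The plan divides by 400, states no correlation, and would need r of about 0.87 to arrive at f = 0.25.

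The wording is also loose. Both figures are upper bounds, and the difference is described as taking variability into account, so 100 might conceivably be the SD of the group means. But both documents call it a difference between groups, and that reading implies a 200-point difference that appears nowhere. As an upper bound, 100 cannot support powering for 200. Nor does the plan present 0.25 as a conventional medium f; it says the value was calculated from the publication.

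The mismatch between 128 and 130 has no practical consequence and is only a matter of tidying.

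**Conclusion.** The concern holds. The printed power is a correct calculation for f = 0.25, but the plan's own derivation gives f = 0.125. For a 100-point difference and SD 400, two-sided 5%, two covariates and equal groups, power is 29.3% with 130 completers and 31.9% with 144 analysed, against a stated 80%. Around 506 completers would be needed for 80%. What 130 completers do provide is 80% power for about 198 points.

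The 29% figure rests on reading 100 as a difference in means and 400 as the SD that applies in the adjusted analysis. If 400 is unadjusted, power at N = 130 is 37% for an assumed correlation of 0.5 and 51% for 0.7. The stated 80% has to be corrected before it can be relied on.

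**What to change.** In the protocol's sample-size justification and in SAP 2.3:

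- State that f = d/2 for two equal groups, and that the calculation with f = 0.25 corresponds to d = 0.50.
- Report that 130 completers give 80% power for a difference of about 200 points at SD 400, and about 29% for 100 points.
- Say what the 100 and 400 represent: raw difference or other quantity, and adjusted or unadjusted SD. If baseline correlation is relied on, give its value and source and show the residual SD.
- If 200 points becomes the stated target, justify it. The documents cite a difference of up to 100 points and offer no support for the larger one.
- Make the printed output consistent: N = 128 with lambda 8.0, df 124 and power 0.801, or N = 130 with lambda 8.125, df 126 and power 0.807.

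The cost is wording in two documents. Enrolment, design and analysis need not change. The price is candour: either the stated power falls or the stated detectable difference doubles.
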